2.0 Background and Rationale

To date, children represent a minority of confirmed cases of COVID-19 worldwide, and it is clear that they are less severely ill when infected (critical illness is very rare: ~1% and death remains extremely rare) than their adult counterparts. In Belgium, the last Sciensano report on children and Covid-19 reveals that children only represent 3% of all infections and 1.7% of all hospitalizations (1). Their role in transmission especially the role of asymptomatic children remains however an unresolved question. Children were, at first, suspected to be a motor of the COVID-19 pandemic, in parallel to influenza infection where school attendance plays an important role in amplifying epidemics. However, more and more data highlight huge differences between the two infections. The role of an individual in the transmission is multifactorial and influenced, among other things, by susceptibility to acquire infection, viral load, symptoms, contact patterns in the community, and social behaviour.

Even with the certainty that children can get infected, available data on probability of viral acquisition state that children have about half the risk of acquiring the virus compared to adults (2). These data are supported by information from contact tracing among households and have been reviewed in four different studies (3-6). Seroprevalence studies show also that children, especially less than 10-year old individuals, have lower rate of past infection (7-10).

However, it is unclear if asymptomatic children with positive PCR on saliva are contagious for their peers in primary school settings and if so, what this secondary attack rate is in this school setting. When quantifying viral load, studies have been conflicting and as well limited in their study design, however viral load does not seem to be majorly influenced by age, and viable viral particles have been retrieved from children's upper respiratory tract specimens (11). These laboratory results must be confronted to clinical observation in order to appreciate their significance. Data on that respect are scarce and what is available emerged from contact tracing in households where children tend to be less identified as index cases. But as they are often asymptomatic or mildly symptomatic, they could be underrepresented as index-cases. In school settings, available data are conflicting but highlight that other factors such as age, or, protective measures such as hand hygiene and social distancing have an impact. In France, transmission is described to have taken place in a secondary school, while in a primary school, transmission likely occurred within households and child transmission mainly reflected the

community presence of infections (12). When studies have been undertaken in settings where more strict protective measures were taken, evidence of transmission within school is limited. Some studies identify no secondary cases (13-15). UK surveillance identifies transmission driven solely by adults (16).

Some argue that, as previously said, these data were collected during lockdown and schools' closure or during careful re-opening and do not reflect the true transmission dynamics. A second often used comment is that only secondary cases linked to symptomatic confirmed cases are taken into account and the role of asymptomatic individuals, mainly children, is underestimated and not measured.

On the other hand, one cannot forget the importance of education and school attendance either, as the WHO pointed out recently. The unanswered question on transmission by children can affect political decisions, economical aspects, wellbeing of children and their families as well as their right for education (17).

It seems, for all these reasons, of importance to assess the transmission dynamics within the school's environment that resume to a full activity according to governmental measures, and, to analyse and sequentially address the impact of asymptomatic individuals.

3.0 Objectives and outcomes

The general objective of our study is to describe the transmission dynamics of SARS-CoV-2 in primary schools in Fédération Wallonie-Bruxelles.

3.2 Outcomes

- Infection of a child with SARS-CoV-2 secondary to a classmate
- Infection of an adult school-attender with SARS-CoV-2 secondary to an infected child
- Infection of a child with SARS-CoV-2 secondary to an adult school attender
- Infection of a child with SARS-CoV-2 secondary to a contact outside the school, including the household

3.3 Exploratory outcomes

Exploratory outcomes will be performed pending sufficient or additional resources.

These are anticipated to include assessment of phylogenetic analysis of SARS-CoV-2 in positive salivary tests by a Whole Genome Sequencing (WGS) test. The aim of this exploratory outcome is to determine transmission linkages between cases and reveal transmission patterns inside households and at school, supporting epidemiological investigation.

We will perform WGS tests only on positive rt-PCR salivary tests with a high viral load defined with a Ct lower than 30 (limit of the technique to perform the analysis). Exploratory phylogenetic analysis may involve collaboration with other specialized laboratories and research groups in Belgium and/or abroad. This would involve transfer of coded samples, traceable only by means of a subject identifier.

3.4 Endpoints

- Time varying number and proportion of children infected with SARS-CoV-2 secondary to an asymptomatic infected classmate (transmission rate inside school with the child being the infector).

- Time varying number and proportion of adult school-attenders infected with SARS-CoV-2 secondary to an asymptomatic infected child (transmission rate inside school but from a child to an adult);
- Time varying number and proportion of children infected with SARS-CoV-2 secondary to an infected adult school-attender (transmission rate inside school but from an adult to a child);
- Time varying number and proportion of children infected with SARS-CoV-2 secondary to a household contact or outside the school (transmission rate from in the community).

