1.0 Synopsis

Title	SARS-CoV-2 transmission in Belgian primary schools of the Federation Wallonie - Bruxelles. An epidemiological pilot study.
Study design	Interventional prospective SARS-CoV-2 infection study.
Study duration	Autumn – winter 2020-2021
General objective	Description and quantification of transmission dynamics of SARS-CoV-2 in primary schools.
Specific objectives	
To assess the role of children attending primary school in the spread of SARS-CoV2 during the 2020-2021 pandemic
 
 • To assess transmission from asymptomatic infected children to other children attending the same school • To assess transmission from asymptomatic infected children to adults (parents and teachers) • To assess transmission from asymptomatic infected adult within the school environment to a child • To assess if a laboratory confirmed case in a classroom has been infected outside the school
Study hypothesis	The investigators hypothesize that children are less likely to become infected in the school environment, compared to the household or outside the school setting. Primary schools do not play a major role in SARS-CoV-2 spreading. They hypothesize that incidence level in schools is mainly a consequence of community transmission ie. the incidence level in households and that the secondary attack rate in schools remains at least 5 times lower than the transmission level in households.
Outcomes	
 • Infection of a child with SARS-CoV-2 secondary to a classmate • Infection of an adult with SARS-CoV-2 secondary to a child • Infection of a child with SARS-CoV-2 secondary to an adult within the school • Infection of a child with SARS-CoV -2 secondary to a household contact or outside the school
Exploratory outcome	Phylogenetic analysis of the SARS-CoV-2 in positive salivary tests by a Whole Genome Sequencing (WGS) test. The aim of this exploratory outcome is to determine potential linkages between cases.

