Endpoints	
 - Time varying number and proportion of children infected with SARS-CoV-2 secondary to an infected classmate (transmission rate inside school but from a child to a child). - Time varying number and proportion of adult school-attenders infected with SARS-CoV-2 secondary to an asymptomatic infected child (transmission rate inside school but from a child to an adult); - Time varying number and proportion of children infected with SARS-CoV-2 secondary to an infected adult school attender (transmission rate inside school but from an adult to a child);

	
 - Time varying number and proportion of children infected with SARS-CoV -2 secondary to a household contact or outside the school (transmission rate from outside school).
Statistical analyses plan	
Sample size determination
 
As a pilot study, no formal sample size calculation was performed. The expected number of children is 2400, the expected number of adult school attenders is 200, and the expected number of classes is 72.
 
Initial incidence and then secondary attack rates will be calculated and compared between gender, across age, and between the three kinds of schools using Poisson or Binomial negative regression if overdispersion. Analyses will be weighted to correct for cluster effect of classes (ICC=0.09).

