7.0 Statistical analyses plan

7.1 Sample size and statistical analysis

As a pilot study, no formal sample size determination was performed. The expected number of children is 2400 (4 times 200 plus 4 times 400), the expected number of adult school attenders is 200, and the expected number of classes is 72. With an incidence around 0.5-1%, the expected number of cases is 120-240. Initial incidence and then secondary attack rates (as transmission estimator) will be calculated and compared between gender, across age, and between the three kinds of schools using Poisson or Binomial negative regression if overdispersion. Characteristics of classes will be compared between schools using ANOVA with F-tests for continuous variable and chi-square or Fisher exact tests for discrete variables. Any significant difference will be considered for correlation with incidence rates (per classes) and attack rates within the Poisson or Binomial negative regression. A cluster effect (Rho = 1.09 or ICC=0.09) will be assessed for weighting data analysis. Estimates will be presented with their 95% Confidence interval. Differences will be presented as absolute and relative differences.

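### The child-to-child endpoint counts only classmate sources (in section 3.4 only asymptomatic ones) although the objectives are school-wide, and the attack-rate denominator is not stated

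*Combined protocol and SAP*

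**What the plan says.** The objectives are school-wide. The synopsis sets out "To assess transmission from asymptomatic infected children to other children attending the same school", and section 3.1 aims at spread between children in primary schools without mentioning class or symptoms.

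The outcome and the endpoints are narrower:

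- Section 3.2, outcome: "Infection of a child with SARS-CoV-2 secondary to a classmate".
- Section 1.0, synopsis endpoint: "secondary to an infected classmate (transmission rate inside school but from a child to a child".
- Section 3.4, endpoint: "Time varying number and proportion of children infected with SARS-CoV-2 secondary to an asymptomatic infected classmate", explained in brackets as "transmission rate inside school with the child being the infector".

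The other three endpoints are child to adult (asymptomatic child source, in both the synopsis and section 3.4), adult to child in school, and household or outside school. The term classmate is not defined.

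For analysis, section 7.1 says that "secondary attack rates (as transmission estimator) will be calculated and compared between gender, across age, and between the three kinds of schools". It gives no numerator, denominator or time window. Section 4.4.3.1 defines positive, asymptomatic and symptomatic cases, but not index or secondary cases.

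**The concern.** The study is meant to describe and quantify transmission in primary schools. If its main in-school endpoint leaves out some routes between pupils, the in-school total is too low by construction, and the hypothesis is that this total is small.

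Pupils of different classes may well meet. The teacher questionnaire in section 5.1 asks whether daycare before and after school mixes all classes. An infection acquired there from a pupil of another class is neither from a classmate, nor from an adult, nor from outside the school.

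The asymptomatic condition raises the same problem. Section 4.4.3.1 does not tie symptom status to the time of transmission, so a child who infects a classmate and later declares symptoms could be classed as symptomatic and drop out of the section 3.4 endpoint.

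The open denominator matters because attack rates are to be compared between kinds of schools, and school size is one of the three selection criteria.

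**Working it through.** **Which infections each wording counts**

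| Source of a child's infection | Objective, 1.0 | Objective, 3.1 | Endpoint, 1.0 | Endpoint, 3.4 |
|---|---|---|---|---|
| Asymptomatic classmate | yes | yes | yes | yes |
| Symptomatic classmate | no | yes | yes | no |
| Asymptomatic pupil, other class | yes | yes | no | no |
| Symptomatic pupil, other class | no | yes | no | no |

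On the literal wording, neither endpoint matches either objective. The synopsis pairs an asymptomatic objective with an endpoint for any infected classmate; sections 3.1 and 3.4 do the reverse. The other-class rows fit no endpoint in either place.

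**Inputs (section 7.1)**

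- Children: "The expected number of children is 2400 (4 times 200 plus 4 times 400"). Check: 4 × 200 + 4 × 400 = 2400, which reproduces.
- Classes: "the expected number of classes is 72". Check: 4 × 6 + 4 × 12 = 72, which reproduces if small schools have one class and large schools two in each of six grades (assumption).
- Mean class size: 2400/72 = 33.33, so 32.33 classmates per pupil.
- Schoolmates per pupil: 199 in a school of 200, 399 in a school of 400.

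**Denominator**

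Classmates are 32.33/199 = 16.2% of schoolmates in a small school and 32.33/399 = 8.1% in a large one. These are shares of pupils, not of contacts or of transmission.

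One secondary case in the index child's class gives:

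- class denominator: 1/32.33 = 3.1%
- school of 200: 1/199 = 0.50%, a ratio of 199/32.33 = 6.2
- school of 400: 1/399 = 0.25%, a ratio of 399/32.33 = 12.3

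These ratios assume that no infection crosses classes. If a share b does, the in-class rate exceeds the whole-school rate by (1 − b)(N − 1)/32.33:

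| b (assumption) | School of 200 | School of 400 |
|---|---|---|
| 0 | 6.2 | 12.3 |
| 0.5 | 3.1 | 6.2 |
| 0.8 | 1.2 | 2.5 |
| pupil shares (0.84; 0.92) | 1.0 | 1.0 |

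**Small versus large schools**

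With a whole-school denominator, the same number of secondary cases per index case gives a rate 399/199 = 2.0 times lower in the large school. This holds only if that number is indeed the same in both.

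**Chance links**

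The incidence of 0.5–1% in section 7.1 has no time unit. Assuming independence and full participation, the chance that at least one schoolmate is positive in a given week is 1 − (1 − p)^(N − 1):

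- 0.5–1% taken as weekly: 63–86% (school of 200), 86–98% (school of 400)
- 0.5–1% taken as the six-week total: 15–28% and 28–49%

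So a school-wide link based on timing alone would often be coincidence.

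**The case against.** The brackets in the synopsis and section 3.4 speak of transmission inside school, and the objectives are school-wide, so the authors may well have meant classmate loosely. This stands as a possible reading. It does not settle the matter, because classmate appears in all three places and is never defined.

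The focus on asymptomatic sources is deliberate: the background asks about them, and section 5.0 says that symptomatic cases would be excluded from schools. That explains the restriction in section 3.4. It does not explain why the synopsis endpoint, the section 3.2 outcome and the section 3.1 objective lack it.

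The plan also collects data from which sources could be traced: weekly PCR, class codes, contact and social-contact questionnaires, diaries, interviews after absence, and sequencing. This is right, and it makes the fix cheap. What is missing is a statement of how these data lead to an endpoint category. The annexed questionnaires are listed by title only and could not be checked.

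The fold-ratios set an in-class numerator against a whole-school denominator, a rate that nobody proposes, and they fall to 1 if spread follows pupil shares. This objection stands in full: the ratios illustrate the ambiguity and do not measure a bias.

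Finally, this is a descriptive pilot. That accounts for the absence of a formal sample size, but not for endpoints that differ between sections.

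**Conclusion.** The point holds for the endpoint wording. Read literally, the child-to-child endpoint omits infections from pupils of other classes and, under section 3.4, from symptomatic classmates. Both belong to the section 3.1 objective, so that count could only be too low. The size is unknown because the cross-class share is not given. The missing attack-rate denominator is a lesser gap, but it should be closed because section 7.1 plans to compare schools.

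Stronger readings are not supported:

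- *Cross-class infections will be counted as outside school.* No passage moves them there, and the school-wide reading remains open.
- *The attack rate is wrong by 6- to 12-fold, or the five-fold hypothesis in the synopsis fails.* The ratio depends on an unknown share and can be 1. The documents give no household attack rate, so nothing follows about the hypothesis.
- *The contact definition in section 4.4.3.2 is a faulty attribution rule.* It follows the national definition and is tied to no endpoint.
- *Section 5.0 commits to sequencing whatever the resources.* It labels sequencing exploratory, and section 3.3 makes exploratory outcomes depend on resources.

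Nor is the direction of error in linking cases established: chance links could raise the in-school count.

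**What to change.** These changes are for analysis only and leave national contact procedures unchanged.

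1. In the synopsis, section 3.2 and section 3.4, define the endpoint as infection secondary to a child attending the same school. Report same class and other class separately, each with its own denominator of participating pupils not yet positive. Report asymptomatic and symptomatic sources separately, so that the objectives and endpoints agree, and apply the same source-status rule to the child-to-adult endpoint.
2. Link cases in all three in-school directions (child to child, child to adult, adult to child) from PCR dates and class codes. State the linking window, vary it in a sensitivity analysis (for example one versus two weekly rounds), and report positives from the same round as order unknown. Support links with the contact questionnaires, diaries, the section 5.0 interviews and sequencing where available.
3. Classify each infected participant as child source in school, adult source in school, outside only, more than one possible, or none known. Report the school share as a range, with the last two groups assigned each way.

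The cost is SAP wording and modest linkage of data already planned. The downside is a visible unresolved group and a wider range. Other-class links without a recorded shared setting should be presented as weak evidence, since many would arise by chance.

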4.0 Methodology

4.1 Study design

This study is an interventional prospective SARS-CoV-2 infection study.

4.2 Study Period

The study will be conducted during the autumn-winter season 2020-2021 and we expect to start on 15th November 2020.

4.3 Selection of participating schools

All Belgian primary schools of the Federation Wallonie – Bruxelles that have organized a resumption of school activities with the social control measures recommended by the government, are eligible for the study. All children and school attenders attending included schools will be eligible to participate.

Each participating school will be considered as a statistical cluster because children within a school share more correlation together than with children from other schools (children are not an independent and identically distributed (i.i.d.) sample) and an intraclass coefficient (ICC) of 9% will be used in analysis.

We will enrol schools according to the following three criteria:

- School size: small school versus a large one

- Incidence of Sars-CoV-2 infection during the first wave of the pandemic in April 2020
 - Regions/cities with a low incidence (from 1.5 to 4.9 per thousand inhabitants on May 6th, 2020)
 - Regions/cities with a high incidence (from 5.0 to 7.5 per thousand inhabitants on May 6th, 2020)
- Socio-economic level of the school: low socio-economic level versus high level, based on ISE that is an official Belgian 20-point-scale index for all schools of the Federation Wallonie-Bruxelles (FWB).

Crossing those three criteria leads to eight categories of schools and one school of each category will be sampled

- Small school - very low incidence city - low socio-economic level
- Small school - very low incidence city - high socio-economic level
- Small school - very high incidence city - low socio-economic level
- Small school - very high incidence city - high socio-economic level
- Large school - very low incidence city - low socio-economic level
- Large school - very low incidence city - high socio-economic level
- Large school - very high incidence city - low socio-economic level
- Large school - very high incidence city - high socio-economic level

According to the definition of the FWB, investigators consider a small school a school with less than 300 children enrolled in the school and a large one a school with more than 300 children.

To determine regions with the highest and lowest incidence of SARS-CoV-2 infection during the first pandemic wave in Belgium investigators will refer to the epidemiological reports of Sciensano: <https://covid-19.sciensano.be/fr/covid-19-situation-epidemiologique>

Written agreement to proceed has been provided by the Ministry of Education and all concerned “Réseaux d’enseignements” in Fédération Wallonie-Bruxelles. Each school of the FWB is followed by a health promotion team (PSE: promotion de la santé à l’école). Physicians from these teams will propose a purposive sample of schools to enter into the study. A

principal investigator, subinvestigator or a PSE team member will contact the school's director and the organizing committee. In case of refusal, another school of the same category will be invited to participate. The participation of schools will be voluntary.

4.4 Study population

All children registered and attending selected primary schools of the Fédération Wallonie - Bruxelles and all adult's school attenders working in the same selected schools will be the study participants.

4.4.1 Inclusion criteria

- All children registered and attended the selected primary schools of the Fédération Wallonie - Bruxelles and adult's school attenders working in the same selected schools.
- Signed informed assent form by child and informed consent form by theirs parents (or legal guardian) and by adult's school attenders before enrolment

4.4.2 Exclusion criteria

Refusal or absence to provide written informed consent before enrolment

4.4.3 Definitions

4.4.3.1 Asymptomatic versus symptomatic cases

- A positive case: a participant who has a positive PCR salivary test for SARS-CoV-2 detected by systematic weekly screening
- Asymptomatic case: a participant who has a positive salivary test for SARS-CoV-2 during the study period and who did not declare any symptoms compatible with COVID-19
- Symptomatic case: a participant who has a positive salivary test with symptoms compatible with COVID-19 during the study period

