5.0 Conduct of the study

Parents and children attending selected schools will be informed of the exact nature of the study with a written version of participant information transmitted by the school director. Parents and children will be invited to participate in a virtual zoom (professional version with secured password) meeting. During this meeting the study objectives, procedures and implications will be explained to the teachers, parents and children. Where/When feasible a

video adapted to each school will be posted on the virtual school platform to be able to reach the maximum of parents and children. Written informed consent will then be obtained from the participants and/or their legal guardian.

Once a week and for six consecutive weeks, all participants of the school will be invited to provide a self-sampled salivary specimen, in the schools and under supervision of medical students on contract.

Currently, procedures only identify symptomatic cases. Interferences with current guidelines will impact results of this study as symptomatic cases and asymptomatic participants with a high-risk contact would be excluded from schools. Indeed, systematic saliva samples will not

Results of the salivary PCR SARS-CoV2 will not be communicated to participants during the study period. Salivary samples of the study will not be analysed routinely but will be treated in batch according to the laboratory capacity of the national platform BIS. The estimated time between sample collection and the availability of the result will be more than a week. Clinical relevance and societal repercussions of the communication to a participant of a positive result so long afterward will be irrelevant. Indeed, it is currently recognized by most experts that contagiousness lasts 7 days after the onset of symptoms. In a study from Taiwan of 100 COVID-19 cases and 2761 close-contacts, secondary attack rates was significantly higher among contacts whose exposure to the index case started within 5 days of symptom onset compared with those exposed later (no secondary cases among the 852 contacts exposed to index case after day 6 of symptom onset) (18).

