It is important to stress that participation to the present study does not exclude participants to follow the national recommendations as detailed in Sciensano procedures, namely a test performing in case of compatible symptoms of SARS-CoV-2 infection or a quarantine in case of a high-risk contact. Investigators will also insist to students and school attenders on the importance of non-pharmaceutical interventions, including physical distancing and mask to prevent SARS-CoV-2 transmission as recommended by Sciensano.

Protocols (ONE as in the Ministry of Education's circular) will be applied as per the standard procedures. The decision to close a classroom will be taken by the PSE and if needed after concertation with the hygiene control inspector of COCOM or AVIQ.

To investigate a possible link between the absence from school of a participant and SARS-CoV-2 infection, the PSE team member will interview this participant later. This interview will continue until 2 weeks after the end of the study to complete data collection.

Any salivary PCR SARS-CoV2 test that comes back positive (with a maximum Ct of 30) will be analysed by a Whole Genome Sequencing (WGS) of the SARS-CoV2 virus (exploratory outcome). Phylogenetic analysis of the virus is expected to determine transmission linkages between cases and to map transmission patterns inside households and at school.

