5.1 Inclusion day

All participants, children and adults school attenders, will be tested at the inclusion day with

- a salivary SARS-CoV2 PCR test collected in the school, under investigators supervision
- a rapid serological test by finger prick (AVIOQ[®]) to determine the seroprevalence of SARS-CoV-2
- All participants (children and adult school attenders) will be invited to complete an electronic questionnaire when possible and a paperback questionnaire otherwise.

The questionnaire will address the following information (see attached file) partially inspired of the questionnaire used in the prevalence study *“Prevalence and incidence of antibodies against SARS-COV-2 in children measured for one year in Belgium: a sero-epidemiological prospective cohort study”* (study coordinator: [name], Sciensano).

- Socio-demographic data: gender, birth date, home postal code, a contact email address, a contact mobile number, country of birth of child and parents
- Housing information: number of people in the household, number of siblings, number of sleeping rooms, distance between school and home
- Exposition information: pre- and after-school daycare attending, extracurricular activities, parent's profession, transportation means between home and school

The salivary SARS-CoV2 sample will be performed at school by the participant him or herself under the supervision of the subinvestigators (80 medical students on contract) for minor

participants. An explanatory film on the method of self-performing the saliva sample will be provided to participants. The children and the teachers will use a garling method to produce saliva. The full procedure is explained in the explanatory film. The participant will wear an adapted mask while gargling. A full explanation of the used gargling sampling technic is also well detailed in the attached paper (19)

The procedure will be performed in a well-ventilated space one participant at a time. The medical student who will collect the sample will wear adapted personal protective equipment (PPE) in order to reduce the risk of transmission to as good as 0. The PPE will include FFP2 mask, gloves, glasses and a protective gown.

After collection, salivary samples will be transported to one of the three participating laboratories (UCLouvain - ULiège - ULB) by the medical student.

Teachers of each class will be invited to complete a questionnaire once with the following questions

- Number of children in the classroom

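### Applied literally, the weekly-screening case definition leaves out infections confirmed only by a test outside the study, and it is not reconciled with the planned absence interview

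*Combined protocol and SAP*

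**What the plan says.** Section 4.4.3.1 gives three definitions. A positive case is "a participant who has a positive PCR salivary test for SARS-CoV-2 detected by systematic weekly screening". A symptomatic case is "a participant who has a positive salivary test with symptoms compatible with COVID-19 during the study period", and an asymptomatic case is the same without declared symptoms. Only the first of the three names the weekly screening.

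The sampling takes place at school. Section 5.0 states that "all participants of the school will be invited to provide a self-sampled salivary specimen, in the schools", and Section 5.1 describes the inclusion sample as "a salivary SARS-CoV2 PCR test collected in the school, under investigators supervision".

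Section 5.0 acknowledges that current guidelines will affect the results, because symptomatic cases and asymptomatic high-risk contacts are kept out of school. It also makes clear that participants remain under the national procedures: "a test performing in case of compatible symptoms of SARS-CoV-2 infection or a quarantine in case of a high-risk contact". Closing a classroom also remains possible.

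Section 5.0 then plans a follow-up of absentees. "To investigate a possible link between the absence from school of a participant and SARS-CoV-2 infection", a member of the school health team interviews the participant later. "This interview will continue until 2 weeks after the end of the study to complete data collection".

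The outcomes in 3.2 and the endpoints in 3.4 are worded as infection and infected persons. Section 7.1 calculates incidence and secondary attack rates.

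**The concern.** The case definition depends on a sample that a participant can give only when present at school. The reasons for absence that the plan itself names, symptoms and a recognised high-risk contact, are tied to the chance of being infected. A participant who falls ill, stays at home, tests positive elsewhere and returns with negative study samples is a known infection that the positive-case definition does not admit. The plan sends someone to ask about exactly that infection, but does not say how the answer enters the case count.

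All four endpoints are at stake. Each is a number and a proportion of infected people. The central hypothesis (Sections 1.0 and 3.1) compares transmission in school with transmission in households or outside, with a factor of at least 5. A selective loss of known infections can distort each side of that comparison, and nothing in the plan makes the loss equal on both sides.

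**Working it through.** The plan gives no figure for the share of infections that would be confirmed only outside the study, so there is none to reproduce. The check is mainly a reading of the sections against each other.

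**Step 1: follow one participant.** Take a participant who is absent with symptoms, has a positive test under the national procedures, and whose study samples are all negative or not taken.

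| Section | Result for this participant |
|---|---|
| 4.4.3.1, positive case | Not a case: not found by the weekly screening |
| 4.4.3.1, symptomatic case | Not a case if the outside test was not on saliva; arguable if it was |
| 5.0, absence interview | Infection is asked about; use of the answer not stated |
| 3.2 and 3.4 | Worded as infection, so they depend on 4.4.3.1 |
| 7.1 | Incidence and attack rates follow from whichever count is used |

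The same reading applies to a quarantined contact without symptoms who has a positive outside test.

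**Step 2: who is left out.** By the plan's own account in 5.0, the absent are symptomatic participants and high-risk contacts. They are not a random subset of the infected.

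**Step 3: which endpoints are touched.**

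- As a secondary case, the participant is missing from the numerator of whichever of the four endpoints applies.
- As an index case, the effect depends on the endpoint. Section 3.4 limits the infector to asymptomatic children in the two child-infector endpoints, so a symptomatic child is out of those by design. The adult-to-child endpoint has no such limit, so a symptomatic adult confirmed only outside would be lost as a source.
- The outside-school endpoint is exposed because a child with a recognised household contact is quarantined, and so misses school sampling. A recognised contact within school can be quarantined too, so the in-school endpoints are exposed as well.

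**Step 4: can the direction be fixed?** Let R be the true ratio of outside to in-school infection, and m_out and m_school the shares of each that are confirmed only outside the study. With those infections not counted and denominators unchanged:

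observed ratio = R × (1 − m_out) / (1 − m_school)

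R = 5 is the hypothesised factor. The shares are assumptions, each taken from 10% to 50%, with no source in the documents.

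- m_out = 50%, m_school = 10%: 5 × 0.50 / 0.90 = 2.8
- equal shares: 5.0
- m_out = 10%, m_school = 50%: 5 × 0.90 / 0.50 = 9.0

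The ratio can move either way or stay put. This shows only that the direction is open. It does not estimate the bias, and it ignores the further effect of lost index cases.

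**The case against.** The strongest reply is that Section 4.4.3.1 does state a rule: a positive case is one found by weekly screening. A screening-only count has a clear rationale, since the study aims to address asymptomatic individuals and Section 5.0 notes that usual procedures find only symptomatic ones. Adding symptom-driven tests mixes two routes of detection. This stands, and a reader should not infer that the plan lacks a counting rule. The difficulty is that the stated rule gives a selectively incomplete count, while the absence interview gathers the missing information without a stated use.

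Two further readings go beyond the documents. One is that all three definitions are confined to study saliva; only the first is, and the school setting of the other two is inferred from 5.0 and 5.1. The other is that the synopsis objective "To assess if a laboratory confirmed case in a classroom has been infected outside the school", or the word infection in 3.2 and 3.4, contradicts the definition. It does not: a positive saliva PCR is itself a laboratory confirmation, and 4.4.3.1 can serve as the working definition of infection.

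It is also fair to say that part of the evidence cannot be seen. The questionnaires are annexed but not reproduced, and one sentence in 5.0 breaks off. The items listed in the synopsis and in 5.2 do not include the participant's own outside result, but that does not establish that the annexes lack it. Even if they record it, a questionnaire item collects data and does not decide what counts as a case.

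**Conclusion.** The point holds in this form: the literal case definition omits infections confirmed only by an outside test during an absence, the omission is selective, and 4.4.3.1 and the absence interview in 5.0 must be reconciled. Incidence, secondary attack rates and the school-versus-outside comparison can be biased as a result. It should be fixed before analysis.

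The conclusion rests on two things: reading the positive-case definition as written, and the plan's own statement about who is kept out of school. It assumes that at least some such participants are confirmed outside and not also found by a study sample.

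Size and direction cannot be derived from the documents. A reader might infer that the omission favours the hypothesis that schools matter little, or that it changes the verdict on the factor of 5. Neither is supported. The restriction to asymptomatic child infectors is a design choice and no part of this point. The lack of a stated weekly denominator in 7.1 is missing detail and is not needed for the conclusion.

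**What to change.** - In 4.4.3.1, add as a case any participant with a documented positive SARS-CoV-2 test made outside the study during the study period.
- Record the date and route of detection through the absence interview already planned, and through one weekly questionnaire item if the annexes do not have one.
- Count these infections as secondary cases in all four endpoints, and as index cases only where the infector restriction of the endpoint allows.
- Report every endpoint twice, with all documented cases and with screening-detected cases only, and name in advance which is primary. Either choice can be defended.

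The cost is a change of wording, possibly one questionnaire item, and one extra analysis. The change concerns counting only and leaves testing and quarantine procedures as they are. It has limits: outside tests are symptom-driven, may use other specimens and are partly self-reported, and quarantined contacts who are never tested remain missing under either count.
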